**Table 6-2 Assessment schedule (Study Part Two)**

Visit No.*	Visit 201A 	Visit 201B 	Visit 211 	Visit 212 	Visit 202	Visit 203	Visit 204...	Study Completion or Premature DC 	FU 3 
Study month	Day1 	Day1  (First Dose Monitor)	Month 1 	Month 3 	Month +6/6	Month +12/12	Every 6 Months until SC		
Informed consent 	XS	XS							
Demography 	S1	S1							
Inclusion/exclusion criteria	XS	XS							
Previous Study	XS	XS							

Details 									
Medical History 	S1	S1							
Concomitant meds	XS	XS	XS	XS	XS	XS	XS	XS	XS
Physical/ neurological exam	S1	S1	S	S	S	S	S	S	S
Skin exam by a qualified physician 		Record in source as needed							
Eye Exam 	S1	S1		S	S				
OCT/Ophthalmic Exam				S 	S 				
PFTs		Record in source as needed							
Vital signs	S1	S1	XS	XS	XS	XS	XS	XS	XS
Hematology/ Chemistry/ Pregnancy 			S	S	S	S	S	S	S
Dispense study drug	S	S		S	S	S	S		
Collect unused study drug			S	S	S	S	S	S	
First dose monitoring 		XS	Record as needed						
First Dose ECG 		XS							
Dosage Administration Record	XS	XS		XS	XS	XS	XS	XS	
MS relapse	XS	XS	XS	XS	XS	XS	XS	XS	XS
Steroid Use	XS	XS	XS	XS	XS	XS	XS	XS	XS
Adverse events/ SAEs	XS	XS	XS	XS	XS	XS	XS	XS	XS
Study Completion								XS	

1. Visit 201A is applicable for current patients or those transitioning from another open-label fingolimod study
2. Visits 201B, 211 and 212 are applicable only for those patients transitioning from a blinded fingolimod study which has comparator treatment arms (placebo, or active comparator, e.g. study CFTY720D2312), from the comparator arm of an unblinded fingolimod study, or for patients who have interrupted treatment for durations as outlined in Appendix 4.
3. Informed consent, demography, previous study details, and medical history are only applicable if the patient enters Study Part Two from another study (i.e., not applicable for patients transitioning from Study Part One).
4. A qualified physician includes a dermatologist OR a physician who has participated in a licensed training program.
5. To be performed by the treating physician.
6. A 3-month and 6-month OCT scan will be done by an ophthalmologist for patients who enroll into this trial from any blinded study which has comparator treatment arms (placebo or active comparator, e.g. study

CFTY720D2312) OR for any patient who has been off fingolimod treatment for 90 days or greater. Then, to be recorded if performed.
7. Tests will be analyzed locally; results will not be recorded in the eCRF, but will remain as source documentation for ongoing safety assessment (clinically significant lab abnormalities should be reported as AEs).
8. First dose 12 lead ECGs (pre- and 6 hours post-dose) to be obtained only for those patients transitioning from a blinded fingolimod study which has comparator treatment arms (placebo, or active comparator, e.g. study CFTY720D2312), from the comparator arm of an unblinded fingolimod study, or for patients who have interrupted treatment for durations as outlined in Appendix 4.
9. The Study Completion (SC) assessments to be performed if a patient has prematurely discontinued or if completed the study per protocol.
10. Extension follow-up visit (EFU) should be scheduled 3 months (+/- 14 days) after the last dose of study medication. The follow-up visit should be done only for patients who have stopped the study but do not continue onto fingolimod, either in a study or non-study setting.
* At each visit the patient must be reminded of the importance of remaining vigilant for infections and, in women of child-bearing age, practicing contraception per protocol.

In addition to the above scheduled visits, patients may have unscheduled visits following an onset of MS relapse or for other reasons as necessary. All information should be collected per Unscheduled Visit eCRFs.

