## 3 Investigational plan

### 3.1 Study design

This study uses an open-label, multi-center, single treatment arm design allowing patients participating in the fingolimod multiple sclerosis clinical development program to enroll in order to collect additional long-term safety, tolerability, efficacy, and health outcomes data.

This study has two parts:

[figure not shown]
- Part One, collecting long-term safety, tolerability, efficacy, and health outcomes data through approximately 30-Jun-2016, and
- Part Two\*, collecting limited safety data until approximately 30-Jun-2018, in a subset of patients participating in Part One, and other eligible patients from ongoing fingolimod trials (e.g., CFTY720D2312).

\*Eligibility for Part Two is defined as prior fingolimod study patients who are unable to obtain fingolimod outside a clinical trial.

By June 2016, investigators must determine commercial Gilenya eligibility for all active study patients (i.e., reimbursed for commercial Gilenya). Patients able to obtain commercial Gilenya will then have their End of Study (Part One) visit and exit the study, regardless of their post-study treatment decision (i.e., continuing on Gilenya commercially or transitioning to another treatment option). Patients discontinuing or completing the study at Part One who do not continue on commercial Gilenya must return for two follow-up study visits, 3-months and 6-months post-last dose of fingolimod. Patients who choose to continue on commercial Gilenya outside the study are exempted from the follow-up visits.

Patients not eligible for reimbursed, commercial Gilenya will be offered continued study participation in Part Two until their scheduled study visit closest to 30-Jun-2018 (+/- 30 day visit window), with a reduced assessment schedule (see Table 6-2), for the purpose of collecting additional long-term safety and tolerability data in support of the primary study objective. Patients discontinuing or completing the study after entering Part Two who do not continue on commercial Gilenya must return for one follow-up study visit, 3-months post-last dose of fingolimod. Patients who choose to continue on commercial Gilenya outside the study are exempted from the follow-up visit.

Patients enrolling in either part of the study from blinded studies will remain blinded to the identity of the treatment in the previous study. In order to maintain the blind, the monitoring

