## **6 Visit schedule and assessments**

[Table 6-1](#) and [6-2](#) list all assessments, and indicates with an "X" the visits when they are performed and recorded in the clinical database, with an "S" indicates when a performed

[figure not shown]
assessment is to be recorded on source documentation, and an “S1” indicates that source documentation should be present to confirm the procedure was performed as part of the previous fingolimod trial (Specific to the Baseline visit only). If an “S1” procedure was not performed in the previous trial, it has to be performed at Baseline. Assessments performed at the final visit of the previous fingolimod trial can fulfill the requirements of the Baseline only if they are completed within 14 days of enrollment in CFTY720D2399.

Patients should follow as much as possible the visit schedule with an allowed “visit window” of  $\pm 5$  days for bi-weekly visits, of  $\pm 10$  days for monthly visits, of  $\pm 14$  days for quarterly visits and of  $\pm 30$  days for bi-annual visits. If a visit was performed outside the visit window, any subsequent visits should be performed according to the original visit schedule. In the study, one month is defined as 30 calendar days.

[figure not shown]
Upon availability of the locally approved prescribing information, completion of any additional assessments required by the local label becomes the responsibility of the investigator. The assessments should be completed for all patients, unless prohibited by local regulations. Any findings qualifying as AEs/SAEs should be reported as such.

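### Table 6-2 schedules no pregnancy or blood test at Visit 201B, where a first or restart dose is given, and Part Two has no row for the hepatitis and HbA1c screen

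*Protocol*

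**What the plan says.** Section 6 of the protocol says that Tables 6-1 and 6-2 "list all assessments, and indicates with an" X, S or S1 when each is done. Section 3.1 opens Part Two to some Part One patients and to "other eligible patients from ongoing fingolimod trials (e.g., CFTY720D2312"). Patients who need first-dose monitoring on entry attend Visit 201B. Table 6-2 footnote 2 states: "Visits 201B, 211 and 212 are applicable only for those patients transitioning from a blinded fingolimod study which has comparator treatment arms". It goes on to include those "from the comparator arm of an unblinded fingolimod study, or for patients who have interrupted treatment for durations as outlined in Appendix 4".

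At 201B the table marks the inclusion and exclusion criteria, dispensing, first-dose monitoring and first-dose ECG. The row "Hematology/ Chemistry/ Pregnancy" is blank at 201A and 201B and carries S from Visit 211 (Month 1) onward. Its footnote 7 says only where the tests are analyzed and recorded.

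Exclusion criterion 2 (Section 4.2) defines pregnancy by a positive hCG laboratory test, criterion 8 rests on HbA1c and criterion 14 on hepatitis serology. Sections 6.5.4 and 6.5.4.2 refer to Table 6-1, and not to Table 6-2, for the screening tests.

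**The concern.** Some patients at 201B take fingolimod for the first time, because they come from a placebo or active-comparator arm. Three of the exclusion criteria that must be checked there depend on laboratory results, and the Part Two schedule supplies none of them before the dose. Section 1.1 describes fetal loss and organ defects in animals and an elimination time of about two months. The pregnancy test therefore matters most: a site that works from the grid can give the dose with no scheduled test and find an existing pregnancy only weeks later.

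**Working it through.** The plan states no figure on this point, so the check compares cells and works out the timing.

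**1. The laboratory row, cell by cell.** Table 6-2 has nine visit columns: 201A, 201B, 211, 212, 202, 203, 204 onward, Study Completion and FU3. The row has nine cells: blank, blank, then seven S marks (2 + 7 = 9). Cells and columns match in number, so the blank at 201B is not a shift from the PDF conversion.

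**2. Part One Baseline against 201B.**

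| Item | Table 6-1, Baseline V1 | Table 6-2, Visit 201B |
|---|---|---|
| Inclusion/exclusion criteria | XS | XS |
| Dispensing | S | S |
| First-dose monitoring | XS | XS |
| Physical exam, eye exam, vital signs | S1 | S1 |
| Hematology, chemistry | S1 | blank |
| Pregnancy test | S1 | blank |
| Hepatitis and diabetes screen | XS | no row |

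S1 covers a procedure "performed as part of the previous fingolimod trial (Specific to the Baseline visit only"); if it was not done there, it must be done at Baseline. Because 201B uses S1 for the examinations and vital signs, the blank laboratory cell cannot be read as shorthand for prior-trial results.

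**3. Which criteria the row would serve.** Marking the existing row at 201B would supply the hCG test for criterion 2. It would not supply criteria 8 and 14: the chemistry panel in Section 6.5.4.2 contains random glucose but neither HbA1c nor hepatitis serology. Those need their own row.

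**4. Time to the first scheduled test.** Inputs from Section 6: "one month is defined as 30 calendar days", and monthly visits have a window of 10 days either side.
- Earliest: 30 − 10 = 20 days after the dose.
- Latest: 30 + 10 = 40 days after the dose (study days 21 to 41 if the dosing day is Day 1).
- At one 0.5 mg capsule a day this is about 20 to 40 doses: 20 × 0.5 = 10 mg to 40 × 0.5 = 20 mg.

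**5. An illustrative consequence.** Assume a pregnancy already detectable at 201B, not found by any other route until Visit 211, and drug stopped that day. With elimination of about 2 months = 60 days (Section 1.1), clearance falls at 20 + 60 = 80 to 40 + 60 = 100 days after the first dose. A positive pre-dose test would have meant no dose.

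**The case against.** The strongest reply is that the text protects patients even where the grid does not. Section 5.5.4 has eligibility confirmed before drug is dispensed, Section 8.1 has monitors verify the inclusion and exclusion criteria in full, and Section 6 and Appendix 4 leave local-label tests with the investigator. Criterion 3 requires highly effective contraception. Part One patients have hematology, chemistry and pregnancy tests at Study Completion. All of this stands and limits the harm. None of it schedules a pre-dose test for an entrant from another trial.

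Section 6.5.8 also says that Part Two pregnancy tests are serum where chemistry is taken and urine at other time points. That could be read as a urine test at 201B. But the same section says that tests are done as the tables detail, and Table 6-2 details none there. The point is ambiguous, which is itself a reason to mark the cell.

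Several stronger readings are tempting but not supported:
- A reader might infer that every restart during Part Two returns to 201B, with the last test up to a visit interval old. But 201B is a Day 1 entry column with consent, eligibility and previous-study details. First-dose monitoring is recorded as needed from Visit 211 on, and unscheduled visits exist. Footnote 2 is better read as covering patients who enter Part Two after an interruption.
- A reader might see a contradiction over restarts after pregnancy. Section 6.5.8 already requires a negative serum test first; only a cross-reference is missing.
- Appendix 5 asks for white-cell, neutrophil and lymphocyte counts at each visit, which the blank cell does not meet. This is a weaker conflict, because the passage is about lymphopenia on fingolimod.
- The hypokalaemia and hypomagnesemia trigger for overnight ECG (Section 5.5.4) orders no test, so its lack of a scheduled measurement is not a conflict.

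Finally, a demand for fresh hematology and chemistry at 201B would be stricter than Part One, whose Baseline accepts prior-trial results. That stands, and the fix follows it.

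**Conclusion.** The concern holds as an omission in the Part Two schedule. Patients entering through 201B can receive a first or restart dose with no scheduled pregnancy or blood test until 20 to 40 days later, and Part Two nowhere schedules the screen behind criteria 8 and 14. A reader might infer that the protocol permits dosing of pregnant or unscreened patients. It does not, because eligibility must be confirmed before dispensing; the schedule simply fails to provide the tests on which that confirmation rests.

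The documents do not give the number of patients at 201B, so the size in patients is unknown. The timing rests on the 30-day month and 10-day window; the 80 to 100 days also rest on the assumptions in step 5. No planned analysis changes. Part Two laboratory results stay in source records (Table 6-2 footnote 7, Protocol Section 9.4.1.2), the Part 2 SAP limits its laboratory section (9.2) to a listing of positive pregnancy tests, and its Section 2 keeps patients from D2312 out of all summaries. This is a cheap improvement for patient safety.

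**What to change.** - **Pregnancy:** mark a serum test S at 201B, with the result reviewed before dosing. This goes beyond the S1 of Part One on purpose, since a prior-trial result can be 14 days old.
- **Hematology and chemistry:** mark S1 at 201B. A prior-trial result counts "only if they are completed within 14 days of enrollment in CFTY720D2399"; otherwise the tests are done before dosing.
- **Screening:** for patients entering from another study, at 201A or 201B, add the hepatitis and HbA1c row to Table 6-2; S1 is acceptable.
- **Text:** cite Table 6-2 beside Table 6-1 in Sections 6.5.4 and 6.5.4.2 for these tests.
- **Footnote:** any restart that needs first-dose monitoring at another time has a pre-dose pregnancy test, with a cross-reference to Section 6.5.8.

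The cost is one local pre-dose sample for women, and for other patients only where no recent result exists. The sample may have to be taken a day or two early where the local laboratory cannot report the same day. Entrants without a qualifying result also need the screening tests. In the document it means marks in one row, one added row, two cross-references and a footnote.

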## 6.1 Patient demographics/other baseline characteristics

Patient demographic and baseline characteristic data were collected from the patient during the previous fingolimod study which included: date of birth, age, sex, race, ethnicity, pre-treatments and source of patient referral. Relevant medical history/current medical condition data includes data until the start of study drug. Where possible, diagnosis and not symptoms were recorded. These data will be mapped to this dataset from the patient's previous fingolimod study.

The demography data collected in this study (date of birth and gender) will ensure the patients are linked to their previous study history.

Previous MS history (including history of relapses) was documented in the patient's medical chart and/or in documented dialog with the patient's referring physician. Information relating to a patient's MS history was collected during the previous fingolimod study which included: date of MS diagnosis, date of first MS symptoms, eye history (e.g. optic neuritis, uveitis), MS relapse history and history of medications used to treat MS and will be transferred directly into the database from the patient's previous fingolimod study.

The same information will be collected for any gap between the previous study (core or extension study, e.g. CFTY720D2309 or CFTY720D2309E) and this study.

## 6.2 Previous Study Details

In order to collect accurate information about the patient's previous fingolimod study details, the following records will be collected at the enrollment visit for each patient: the patient's previous fingolimod study number, center number, and patient number.

Upon the implementation of Amendment 4, the following information will be collected: the date of full approval for Amendment 4, whether or not the patient is re-enrolling into this study (defined as a patient who previously completed CFTY720D2399 based on the original study endpoint who is now re-entering the study using the originally assigned patient ID number) and the date of re-enrollment. In addition, data will be collected on any potential treatment gap during the time a patient may have temporarily been out of a fingolimod study and whether or not the patient went onto commercially available medication during the gap, if applicable.

### **6.3 Treatment exposure and compliance**

In order to collect accurate information about the study drug exposure, the following records should be maintained for each patient receiving study medication: records of study medication dispensed and returned, dosages administered and intervals between visits. Appropriate data should be transcribed on the Dosage Administration Record (DAR) eCRF. To allow for accurate study reporting, the DAR will be closed at the completion of Study Part One and a new DAR eCRF will be opened in the Study Part Two.

Compliance will be assessed by the investigator and/or study personnel at each visit using capsule counts and information provided by the patient. A monitor will perform and document drug accountability during site visits and at the end of the study.

### **6.4 Efficacy**

MS relapse activity and neurological impairment of MS as measured by the Expanded Disability Status Scale (EDSS), Magnetic Resonance Imaging (MRI) and by the Multiple Sclerosis Functional Composite (MSFC) will be obtained in Study Part One only in order to characterize the disease activity over the long term.

#### **6.4.1 MS relapse**

General definition of relapse: Appearance of a new neurological abnormality or worsening of previously stable or improving pre-existing neurological abnormality, separated by at least 30 days from onset of a preceding clinical demyelinating event. The abnormality must be present for at least 24 hours and occur in the absence of fever (<37.5°C) or infection.

Definition of confirmed relapse (For Study Part One only): A relapse must be confirmed by an EDSS certified Physician (see [Section 6.4.2](#)). It is recommended that this occur within 7 days of the onset of symptoms. A relapse is confirmed when it is accompanied by an increase of at least half a step (0.5) on the EDSS or an increase of 1 point on two different Functional Systems (FS) of the EDSS or 2 points on one of the FS (excluding Bowel/Bladder or Cerebral FS).

A patient should report symptoms indicative of a MS relapse at a scheduled visit or at any other time during the study. Patients must be instructed to immediately contact the study site if he/she develops new, reoccurring or worsening neurological symptoms. Standard therapy with corticosteroids can be used.

For suspected MS relapses reported by the patients between the scheduled visits, the investigator will determine whether to bring the patient in for an unscheduled visit based on

the patient's condition and standard of care. For patients who come in for an unscheduled visit at the time of the suspected MS relapse, an EDSS evaluation must be performed to verify the relapse. Relapse severity will be determined based on relapse EDSS scores.

Upon receiving a report of symptoms indicative of a relapse, the investigator will assess whether the symptoms occur in the presence of fever or infection. If fever or infection can be excluded, the investigator will determine whether the patient will come in for an unscheduled visit and EDSS evaluation. If fever or infection cannot be excluded, the neurological examination will be postponed until the fever or the infection has ceased, provided that the symptoms indicative of a relapse are still present at that time.

All relapses, confirmed (Study Part One only) and unconfirmed, will be recorded on the Summary of MS Relapses eCRF. Atypical relapses should be documented as adverse events or serious adverse events, depending on severity of relapse.

#### **6.4.2 Expanded Disability Status Scale (EDSS)**

EDSS will be determined only during Study Part One, based on neurological examination at scheduled visits according to [Table 6-1](#) and in the setting of a suspected MS relapse.

EDSS is a scale for assessing neurologic impairment in MS. It is a two-part system including: (1) a series of scores in each of eight functional systems, and (2) the EDSS steps (ranging from 0 (normal) to 10 (death due to MS)). The functional systems are Visual, Brain Stem, Pyramidal, Cerebellar, Sensory, Bowel and Bladder, Cerebral and other functions. It is recommended that fatigue will not be included into the Cerebral score of the EDSS.

For patients coming from phase II/III studies, EDSS will be assessed by a treating physician who has been EDSS trained. A one-time Neurostatus certification is required for all evaluating physicians who have patients enrolled from phase II/III studies. If a new rater is brought on board at any time throughout the study, proof of certification of that rater will be required at that time before any EDSS assessments can be done by the new rater. A certified backup evaluating physician should be appointed to conduct neurological examination ONLY when the primary evaluating physician is unavailable due to illness, vacation, or travel. Blinding of the evaluators is not required in this protocol and the PI can serve as the rater provided training requirements have been met.

For patients who transferred from trials other than the phase II/III trials, the individual functional scores do not need to be collected, and the evaluating physician performing EDSS assessments does not have to carry a certification.

EDSS assessments are detailed in [Table 6-1](#). Refer to [Appendix 8](#) for information on Expanded Disability Status Scale (EDSS).

